At each evaluation, medical and dental history will be updated, an oral exam will be performed, and AEs and SAEs will be assessed and recorded. PD, CAL, and BOP will be evaluated at screening and on Days 15, 30, 60, 90, 180, and 270. Subjects will have urinalysis in addition to blood tests including hematology and chemistry (liver and kidney function) panels done at screening and repeated at Days 90 and 270. FMPI will be recorded at baseline and on Days 15, 30, 60, 90, 180, and 270. Inflammatory cytokines in serum will be measured at baseline and on Days 15, 90, 180, and 270. GCF will be collected and analyzed at baseline and on Days 15, 90, 180, and 270. Microbial analysis of periodontal flora will be performed at baseline and on Days 15, 90, 180, and 270.

At each treatment visit, in addition to administration of ST266 or placebo, medical and dental history will be updated, AEs and SAEs will be assessed and recorded, concomitant medications will be recorded, and oral hygiene instruction will be provided.

Randomization will be stratified by site and smoker status (never smoked or quit smoking more than two years ago vs. has smoked within the last two years). Randomization will be blocked such that assignment to treatment groups both within sites and within smoker status will be

approximately even (1:1:1). ST266 will be supplied to the study site and prepared for use by trained clinical staff, who will not be the same as the dental professionals evaluating the subjects.

**Primary Endpoint:** The primary effectiveness endpoint of this study is the average change in PD from baseline to 9 months (Day 270) in tooth-sites with baseline PD  $\geq$  6mm. This endpoint will be analyzed at the patient level similar to other studies.

**Secondary Endpoints:** Secondary efficacy endpoints of this study are: (1) change from baseline in CAL at 9 months (Day 270) with baseline PD  $\geq$  6mm; (2) change from baseline in BOP at 9 months (Day 270) using whole-mouth average, and (3) change from baseline in PD at 9 months (Day 270) using all tooth-sites.

Baseline refers to the initial measurement of the endpoint, which may occur at the screening or baseline visit according to the schedule of assessments.

**Safety Endpoints:** The safety endpoints are frequency and pattern of AEs and SAEs.

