2. PROTOCOL SUMMARY

Name of Sponsor/Company: Stemnion, Inc.
Name of Investigational Product: ST266 [Amnion-derived Cellular Cytokine Solution (ACCS)]
Title of Study: A randomized, double-blind, placebo-controlled study to evaluate the safety, efficacy, and treatment regimen of ST266 in subjects with moderate to severe periodontitis.
Study Center(s): Multi-center (6 clinical sites in the United States)
Phase of Development: Phase 2a
Objectives: Primary: To determine the efficacy of ST266 to reduce pocket depth (PD) adjunctive to scaling and root planing 270 days after initiation of treatment. Secondary: To determine safety and changes in: 
• Clinical attachment level (CAL)• Bleeding on probing (BOP)
Study Design: The study is a 9-month, randomized, double-blind, parallel-design study of subjects with existing moderate to severe periodontal disease randomly assigned to one of three groups. The primary endpoint of PD change will be evaluated following 270 days on study. Subjects will be followed for 9 months for safety and radiographic evaluations. Subjects who meet inclusion and exclusion criteria will be randomized to one of three treatment groups. Randomization will be stratified by site and smoker status (never smoked or quit smoking more than two years ago vs. has smoked within the last two years). Randomization will be blocked such that assignment to treatment groups both within sites and within smoker status will be approximately even (1:1:1). Treatment will be initiated after scaling and root planing (SRP). All subjects will be evaluated at baseline and Days 1, 15, 30, 60, 90, 180, and 270.
Number of Subjects (Planned): A total of 150 subjects will be enrolled in the study, 50 per group.
Study Duration per Subject: Each subject will be enrolled in the study for 9 months.
Diagnosis and main criteria for inclusion: Moderate to severe periodontal disease according to American Academy of Periodontists (AAP) definition (at least 6 teeth with 6mm or greater pocket depth and 3 mm or greater CAL at baseline). Inclusion Criteria: 
1. Provision of signed, written informed consent prior to participation in any study-related

procedures.

2. Good general health as evidenced by medical history.
3. Between 18 and 85 years of age at time of informed consent signature.
4. Male or female.
5. Minimum of 18 teeth, excluding third molars.

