2.6 Sample Size Determination

One hundred and fifty (150) subjects will be enrolled. The sample size for the study is based on the sample size required to compare treatment with ST266 versus placebo for the primary efficacy endpoint.

The number of subjects was estimated based on two meta-analysis studies that reviewed 50 and 72 articles respectively (Bonito, 2005).

Using the normal approximation for sample size determination for an independent sample t-test, and assuming a PD reduction of 0.5 mm on average (difference in means) with a standard deviation of 0.7 mm, $\alpha=0.05$ (0.025 per comparison, Bonferroni correction), and 85% power, a sample size of 44 per group will be required. The expected dropout rate is approximately 10% based on previous experiments; hence 50 subjects will be enrolled per group.

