3. GENERAL ANALYSIS AND REPORTING CONVENTIONS

For continuous endpoints, the summary statistics will generally include number of subjects with data (n), mean, standard deviation, median, minimum and maximum. No preliminary rounding will be performed; rounding will only occur after analysis. To round, the digit to right of last significant digit will be considered: if < 5 then round down, if ≥ 5 then round up. Means and medians will be presented with one more decimal place than the precision of the data. Standard deviations will be presented with two more decimal places than the precision of the data. Percentages will be presented with one decimal place. Minimums and maximums will be presented with the same precision as the original data.

For categorical endpoints, the summary statistics will generally include: number of subjects randomized and/or dosed, number of subjects with data, and the percentage of those with data in each category. Frequency distributions will be presented as appropriate.

Analysis of the clinical efficacy data will consist of modeling endpoints, including change from baseline in PD, CAL, BOP, and FMPI, with treatment group, patients, smoking status, and investigational site as main effects and adjusting for baseline values of a given endpoint. Post-baseline treatment comparisons will be modeled through a GEE method (with a linear link and exchangeable covariance matrix), adjusting for the baseline value. Methods of analysis for periodontal flora, inflammatory cytokine levels in GCF and in serum, and RBL will be described in separate statistical analysis plans.

Hypothesis testing, unless otherwise indicated, will be two-sided. When confidence intervals are presented, they will be two-sided with a confidence coefficient of 95%. Actual P-values will be reported to 3 decimal places if greater than 0.001. If less than 0.001, the value ' <0.001 ' will be reported.

The statistical software, SAS[®] version 9.3 or above, will be used for all summaries and statistical analyses.

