8.3.1 Primary Efficacy Analyses

The generalized estimating equations (GEE) method with a linear link and exchangeable covariance matrix (within subject correlation structure) will be used to estimate the treatment group effects with respect to change from baseline PD at 270 days, adjusted for baseline PD in tooth-sites with baseline PD ≥ 6 mm. The two primary hypotheses to be tested are:

- 1) The change in PD from baseline (PD ≥ 6 mm) (Screening Visit) at the 270 Day Visit differs between the Group 1 (see section 2.4) and Group 3 (placebo) treatments. Point estimates and 95% confidence intervals will be presented for the

treatment group differences in PD change from baseline at Day 270 by baseline smoker status.;

- 2) The change in PD from baseline (PD ≥ 6 mm) (Screening Visit) at the 270 Day Visit differs between the Group 2 (see section 2.4) and Group 3 (placebo) treatments. Point estimates and 95% confidence intervals will be presented for the treatment group differences in PD change from baseline at Day 270 by baseline smoker status.

SAS code for the GEE model is as follows:

```
proc gee data=Day270dataset
  where (base $\geq$ 6 and ITT Set='Y' and paramcd='PDEPTH');
  class subjid trt01a site smoker_status;
  model chg = trt01a base site smoker_status smoker_status*trt01a;
  repeated sub=subjid /type=exch;
  lsmeans trt01a/pdiff;
run;
```

Where:

- 1) The Day270dataset only includes records for Day 270 visit)
- 2) chg = change from baseline of each individual tooth site
- 3) (base \geq 6 and ittf1='Y' and paramcd='PDEPTH'): subsets the dataset to include only PD outcomes, the ITT population, and tooth sites with baseline PD greater or equal to 6mm.
- 4) chg= change in PD from baseline
- 5) trt01a = treatment group
- 6) site=investigator institution rather than tooth site
- 7) base = baseline PD

The 15-, 30-, and 60-Day visits were not included in the primary statistical model since the tooth-sites at the earlier visits may still be healing from the effects of the SRP procedure with possible SRP-related gingival swelling affecting the PD measures.

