Since there are two primary hypotheses, Bonferroni corrections will control for multiplicity with $p < 0.025$ considered significant. Point estimates and 95% confidence intervals will be presented for the treatment group differences in change from baseline at each assessment time point. These analyses will be performed once all the subjects (excluding those withdrawn) have been unblinded and completed their 270-Day Visit.

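### The primary GEE as coded requests no small-sample correction, so its two 0.025 tests are likely to exceed 5% family-wise error, by an amount that depends on the smoker share

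*SAP*

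**What the plan says.** SAP 8.3.1 gives SAS code for the primary analysis. The response is the Day 270 change in PD at each tooth-site with baseline PD of at least 6 mm. Clustering is set by "repeated sub=subjid /type=exch". The model contains treatment, baseline PD, investigational site, smoker status and smoker status by treatment. The SAP version log shows site and smoking entering in version 3.1 and the interaction in version 3.2. Treatment differences come from an LSMEANS statement with no weighting option.

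For the two regimen-versus-placebo hypotheses, the SAP says "Bonferroni corrections will control for multiplicity with" a threshold of p < 0.025. SAP 3 adds: "Hypothesis testing, unless otherwise indicated, will be two-sided". No section names a standard-error type, a small-sample correction or a reference distribution.

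Protocol 7.1 says of the primary endpoint: "This endpoint will be analyzed at the patient level similar to other studies". Protocol 7.2 and 13 also prescribe GEE, the latter with an exchangeable covariance and baseline adjustment. SAP 2.2 describes the tooth-site model as the means of estimating each patient's average.

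**The concern.** With 150 patients as clusters, large-sample GEE inference looks safe. But the estimate that is tested is an equally weighted average of a smoker and a non-smoker effect, taken from a 12-parameter model. If smokers are a minority of the 50 patients per arm, half of the primary estimate rests on a small group. An uncorrected sandwich variance tends to be too small in that situation, and a normal reference adds to the error. The plan would then claim 0.025 per comparison without delivering it. A regimen could be declared effective too readily, and the primary intervals would be too narrow.

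**Working it through.** **1. The plan's own figure.** Inputs from SAP 2.6: "assuming a PD reduction of 0.5 mm on average (difference in means) with a standard deviation of 0.7 mm", two-sided 0.025 per comparison, "and 85% power, a sample size of 44 per group will be required". The normal approximation is

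n = 2(SD/difference)²(z₀.₉₈₇₅ + z₀.₈₅)² = 2 × (0.7/0.5)² × (2.241 + 1.036)² = 3.92 × 10.74 = 42.1, rounded up to 43.

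The t-test solution is 43.4, which gives the stated 44, with power 85.5%. So the sample size rests on a t-test that holds 0.025 per comparison.

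**2. The target error rate.** Two independent tests at 0.025 give 1 − 0.975² = 4.94%. Two exact tests that share a placebo arm (correlation 0.5) give 4.65%.

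**3. Parameter count.** Intercept 1 + treatment 2 + baseline 1 + centre 5 (six sites, SAP 2) + smoking 1 + interaction 2 = 12. The code has no patient term, although SAP 3 and Table 8-1 list one. The code is followed here.

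**4. Weight on the smoker stratum.** Let s be the smoker share among 50 per arm (SAP 2: "A total of 150 subjects will be enrolled in the study, 50 per group"). Ignoring covariates and uneven tooth-site counts, an equally weighted arm mean has variance σ² × ¼ × [1/(50s) + 1/(50(1 − s))]. Smokers contribute the fraction 1 − s of it. At s = 20%: ¼ × (1/10 + 1/40) = 0.03125, of which 0.025 (80%) comes from 10 patients. The unweighted arm mean would have variance 1/50 = 0.020.

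**5. Simulation under the null.** About 20,000 trials per setting were run (Monte Carlo error about 0.2 points), using:
- six unequal centres and permuted blocks within centre and smoking stratum
- the SAP's exchangeable GEE and equally weighted LSMEANS
- an uncorrected sandwich standard error, rejecting if |z| > 2.241

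Assumptions that the documents do not supply: the smoker share, a within-patient correlation of 0.1 to 0.5, and a variable number of tooth-sites per patient (at least 6, mean 20 or 40). The 120-patient setting is 150 × 0.8, the protocol's 20% dropout with no imputed contribution. The SAP itself says "The expected dropout rate is approximately 10% based on previous experiments" and imputes dropouts, which keeps the count nearer 150.

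| Smoker share | Smokers per arm of 50 | Smoker part of contrast variance | Family-wise error, 150 patients | Family-wise error, 120 patients |
|---|---|---|---|---|
| 50% | 25 | 50% | 6.3% | 6.6% |
| 35% | 17.5 | 65% | 6.5% | 7.1% |
| 20% | 10 | 80% | 8.3% | 9.5% |
| 15% | 7.5 | 85% | 10.2% | not run |
| 10% | 5 | 90% | 15.0% | not run |

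Further runs at 150 patients gave 7.7% to 8.5% at 20% smokers, 5.8% to 6.8% at 35%, and 6.3% to 6.7% at 50%. Coverage of the 95% intervals was about 92% to 94%.

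**6. What drives the excess.**
- Raising the within-patient correlation from 0.1 to 0.5 moves the error only from 6.9% to 6.3%.
- The same tooth-site GEE with treatment and baseline only (the protocol's terms) gives 4.5% to 4.7%. Omitting the stratification factors makes tests somewhat conservative (patient-mean ANCOVA on those data gives 3.7% to 3.8%), but the tooth-site model does not exceed 5%.
- Dropping only the interaction leaves 5.7% to 6.1%.
- Model-based standard errors with a normal reference give 6.1% to 7.4%.

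**7. Remedies on the same designs.**
- Mancl-DeRouen covariance with a t reference: 3.3% to 4.6%.
- Patient-mean ANCOVA with the same terms, including the interaction, and a t reference: 4.0% to 5.1%.
- Scaling the sandwich by N/(N − p) with a t reference: 4.7% to 5.3% at 35% to 50% smokers, but about 6% to 7.5% at 20%. This is not reliable.

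**The case against.** Several points on the other side stand.

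- **The standard error is inferred.** The SAP names neither a sandwich variance nor a normal reference. The strict statement is that they are unspecified. However, the code requests no correction, and the model-based alternative with a normal reference also exceeds 5%.
- **The size is conditional.** At 35% to 50% smokers and 150 patients the excess is modest for a Phase 2a trial. No single range can be read off the documents.
- **The simulation is incomplete.** Worst-value imputation for dropouts and rescued pockets (SAP 8.1.1 and 8.1.2.1) was not modelled.

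A reader might also draw two stronger conclusions that the documents do not support. One is that analysing tooth-sites inflates the error. The REPEATED statement clusters tooth-sites by patient, and the tooth-site GEE with only the protocol's terms does not exceed 5%. The other is that the SAP abandons a patient-level analysis required by the protocol. Protocol 7.1 does use that phrase, but the protocol also prescribes GEE and names no patient-mean ANCOVA for PD. SAP 2.2 connects the two descriptions. This is not a clear departure.

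**Conclusion.** The point holds in conditional form. Run with an uncorrected sandwich standard error and a normal reference, the coded analysis does not deliver 0.025 per comparison. Against a target of at most 5% (4.65% for exact tests), family-wise error at 150 patients is about 6% to 7% with 35% to 50% smokers and about 8% to 9% with 20%, and it rises further below that. With 120 contributing patients and 20% smokers it reaches 9.5%, or about 10% in the least favourable runs. Every smoker share tried exceeded 5%. The figures rest on an assumed smoker share, equal LSMEANS weighting and assumed tooth-site counts. The within-patient correlation matters little. The cause is 12 parameters together with a possibly small stratum carrying half the weight. The defect is worth correcting before unblinding, but it does not invalidate the design.

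**What to change.** In SAP 8.3.1, keep the GEE and the smoker-by-treatment term, and add three statements:

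1. The covariance is a bias-corrected sandwich, for example Mancl-DeRouen.
2. Tests and intervals use a t reference with degrees of freedom based on patients, not tooth-sites.
3. The LSMEANS treatment contrast weights the smoker strata in a named way, either equally or by observed share.

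An acceptable alternative is ANCOVA on each patient's mean PD change over qualifying tooth-sites, with the same terms and a t reference. The interaction must stay in, because SAP 8.3.1 needs smoker-specific estimates and SAP 8.3.2 uses the interaction as a gatekeeper.

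Apply the same choice to CAL, which SAP 8.3.2 analyses with the same model. At the same time, reconcile the patient term listed in SAP 3 and Table 8-1 with the code.

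The cost is a short SAP revision, a few lines of code and somewhat wider intervals.

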## 7.2. Number of Subjects

One hundred and fifty (150) subjects will be enrolled. The sample size for the study is based on the sample size required to reject the null hypothesis for the primary efficacy endpoint which contains two comparisons. Using the normal approximation for sample size determination for two independent samples, t-tests, and assuming a PD reduction of 0.5 mm on average (difference in means) with a standard deviation of 0.7 mm,  $\alpha=0.05$  (Bonferroni corrected,  $\alpha$  0.025 per comparison), and 85% power, a sample size of 44 per group will be required. The expected dropout rate is 20% based on previous experiments and current enrollment trends hence 50 subjects will be enrolled per group. GEE analyses will be performed and therefore, the actual power will be between 85 and 90%.

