2.5 Treatment Group Assignments or Randomization

Randomization will be stratified by site and smoker status (never smoked or quit smoking more than two years ago versus has smoked within the last two years). Randomization will be blocked such that assignment to treatment groups both within sites and within

smoker status will be approximately even (1:1:1). ST266 will be supplied to the study site and prepared for use by trained clinical staff, who will not be the same as the dental professionals evaluating the subjects.

At the 90-Day analysis, one statistician and one programmer will be unblinded in order to generate the unblinded 90-day analysis. Another team of statisticians and programmers will remain blinded until the 270-day analysis at the end of the study.

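### Holm would raise power on the two primary comparisons above plain Bonferroni at the same 0.05 family-wise ceiling, at little cost

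*SAP*

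**What the plan says.** SAP section 8.3.1 states two primary hypotheses on change in pocket depth at Day 270: Group 1 against placebo, and Group 2 against placebo. On multiplicity it says "Since there are two primary hypotheses, Bonferroni corrections will control for multiplicity with" p < 0.025 taken as significant. That threshold applies to each comparison whatever the other one shows.

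The sample size uses the same rule. SAP section 2.6 gives "0.025 per comparison, Bonferroni correction), and 85% power, a sample size of 44 per group will be required", and protocol section 7.2 refers to "the primary efficacy endpoint which contains two comparisons" and names the Bonferroni correction. SAP section 3 adds that "Hypothesis testing, unless otherwise indicated, will be two-sided". Neither document gives a step-down rule or any other way of passing unused alpha from one primary comparison to the other.

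The secondary endpoints have their own rule in SAP section 8.3.2: CAL before BOP, with 0.025 for each regimen comparison. The section does not say whether the step from CAL to BOP is taken separately for each regimen or only after both CAL comparisons succeed. It does not tie the secondary tests to the primary result.

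**The concern.** A fixed 0.025 for both comparisons leaves part of the 0.05 unused whenever one comparison succeeds. If Group 1 against placebo has p < 0.025, that null hypothesis has been rejected and one remains, yet the plan still holds the second comparison to 0.025. A second-comparison p-value between 0.025 and 0.05 would be declared not significant, although a family-wise level of 0.05 allows it to be declared significant.

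This matters here because the title says that the study evaluates the treatment regimen. A conclusion on each regimen is part of its purpose, and that is where the unused alpha would help.

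**Working it through.** **Inputs.** The effect and SD come from SAP section 2.6: "assuming a PD reduction of 0.5 mm on average (difference in means) with a standard deviation of 0.7 mm". Alpha is 0.05 overall and 0.025 per comparison, two-sided, with 85% power (SAP sections 2.6 and 3). Allocation is 1:1:1 (SAP section 2.5) with one placebo arm shared by both comparisons. With equal arm sizes and variances the two test statistics therefore correlate at 0.5. Enrolment is 50 per arm. That leaves 50 × 0.8 = 40 at the protocol's 20% dropout (section 7.2) and 50 × 0.9 = 45 at the SAP's roughly 10% (section 2.6).

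**The plan's figure first.** Normal approximation: n = 2 × [0.7 × (2.241 + 1.036) / 0.5]² = 42.1, so 43 per arm. The two-sample t-test gives power of 84.6% at 43 and 85.5% at 44. The stated 44 reproduces.

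**The two rules.** The expected z-statistic is 0.5 / (0.7 × √(2/n)): 3.19 at n = 40, 3.35 at 44 and 3.57 at 50.
- Bonferroni: reject each comparison if |z| > 2.241.
- Holm: do the same and, if one comparison is rejected, reject the other if |z| > 1.960.

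**Power with 0.5 mm in both regimens** (4 million bivariate normal draws, correlation 0.5), Bonferroni to Holm:

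| Evaluable per arm | Each comparison | Both won | At least one won |
|---|---|---|---|
| 40 | 83.0% to 87.2% | 72.9% to 81.3% | 93.1%, unchanged |
| 44 | 86.6% to 90.3% | 78.2% to 85.5% | 95.1%, unchanged |
| 45 | 87.4% to 91.0% | 79.4% to 86.5% | 95.5%, unchanged |
| 50 | 90.8% to 93.7% | 84.5% to 90.3% | 97.1%, unchanged |

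Check at 44: the two per-comparison powers must sum to the power for at least one plus the power for both. Holm: 2 × 90.3 = 180.6 = 95.1 + 85.5. Bonferroni: 2 × 86.6 = 173.2, against 95.1 + 78.2 = 173.3, which agrees within rounding.

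The last column cannot change, because Holm's first step is the Bonferroni test.

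**Unequal effects** (my assumption: 0.5 and 0.25 mm, 44 per arm): the weaker regimen goes from 28.6% to 38.2% and the stronger from 86.6% to 87.1%.

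**False positives.**
- Both regimens inert: the family-wise error is 4.6% under either rule.
- One regimen at 0.5 mm and the other inert, 44 per arm: the inert regimen is wrongly declared effective 2.5% of the time under Bonferroni and 4.4% under Holm. The effective regimen goes from 86.6% to 86.8%.
- One regimen with a very large effect and the other inert: 2.5% against 5.0%, which is the ceiling.

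**Why the same rule does not carry straight over to CAL and BOP.** Suppose the CAL-to-BOP step runs within each regimen, Group 1 truly improves CAL, and both Group 2 CAL and Group 1 BOP are null. Under the present rule the error bound is 0.025 + 0.025 = 0.05. With Holm within CAL, Group 2 CAL moves to 0.05 once Group 1 CAL succeeds, while Group 1 BOP still uses 0.025, so the bound is 0.075. With CAL and BOP simulated as independent, the secondary family-wise error rises from 4.6% to 6.5% if the CAL effect has the planned standardised size at 44 per arm, and from 4.9% to 7.4% if it is very large. If BOP opens only after both CAL comparisons succeed, the error stays at or below 5%.

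**The case against.** The strongest reply is that nothing here is wrong. Bonferroni is pre-specified, valid and consistent with the sample size. The 85% target is met per comparison: by the normal approximation, power is 86.6% at 44 and 87.4% at 45. In a Phase 2a trial a sponsor may prefer a simple rule. All of that stands.

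The rise from 2.5% to 4.4% in the inert regimen's false-positive rate also stands as a real cost in a trial meant to compare regimens. A reader might infer that Holm changes nothing when only one regimen works. That is not so: only the 0.05 ceiling is the same under both rules.

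A reader might also infer from the protocol's 20% dropout that the primary analysis will have 40 subjects per arm and fall short of 85%. The documents do not support that. SAP section 8.3 analyses the ITT population, and section 8.1.1 carries the worst value forward for subjects who withdraw, so dropouts are not simply removed. The 40 and 45 are evaluable counts in the sense of the sample-size calculation. The conflict between 20% and about 10% dropout is a separate matter to reconcile.

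The usual complaint that Holm lacks simple matching simultaneous intervals is correct but weighs little. SAP sections 3 and 8.3.1 already report 95% intervals that are not adjusted to 0.025.

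**Conclusion.** The point holds as a low-cost improvement to the primary pair. Holm is uniformly more powerful than the planned rule at the same 0.05 ceiling, and its error control does not depend on the correlation between the comparisons. With both regimens at 0.5 mm, the gain is about 3 to 4 percentage points per comparison and 6 to 8 points for winning both, across 40 to 50 per arm.

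Three stronger readings are not supported:
- The present rule is not invalid, and by its own per-comparison target the trial is not undersized at 44.
- Holm does not raise the chance that the trial succeeds on at least one regimen.
- The rule cannot simply be extended to CAL and BOP, because SAP section 8.3.2 leaves open how the step from CAL to BOP works.

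The figures rest on the design's subject-level normal approximation, equal arms and a common SD of 0.7 mm. They do not describe the tooth-site GEE model or the effect of imputation.

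**What to change.** - In SAP section 8.3.1, replace the fixed threshold with this rule: the smaller of the two primary p-values is compared with 0.025 and, if it is significant, the larger is compared with 0.05 (Holm).
- Align the Bonferroni wording in protocol section 7.2. Protocol section 13, which gives only p < 0.05, should refer to the same rule.
- Keep the sample size. 0.025 remains the first-step threshold, so the calculation in SAP section 2.6 still applies.
- Leave CAL and BOP at 0.025 per comparison. Use Holm within those pairs only if SAP section 8.3.2 also states that BOP is tested only after both CAL comparisons succeed.
- If each regimen's 0.025 is meant to pass from its PD test to its own CAL test, write that down first, because that alpha could not also go to the other regimen's PD test.
- Record the change before Day 270 unblinding. SAP section 2.5 provides for one statistician and one programmer to be unblinded for a Day 90 analysis, so the decision should come from people without access to those results.

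The cost is a short edit in each document, with no extra subjects, data or change of model. The sponsor accepts the higher false-positive rate for an inert regimen when the other works, and gives up simple matching simultaneous intervals.
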